5.1. Populations

Intention to Treat (ITT). It is the primary population of the EPIC trial and includes all patients randomized in the study. They will be analyzed according to the group assigned at the randomization visit, regardless of whether they received the medication or not.

Per protocol (PP). All patients who were adherent to the assigned intervention at the time of randomization. In addition, it includes all patients with complete data. It will be considered as a sensitivity analysis.

5.2. Subgroups

No subgroup analysis will be done.

6. Analysis plan

Initially, all the variables will be described according to the intervention groups in the ITT population. Variables with a normal distribution will be summarized with mean and standard deviation (SD), otherwise, they will be shown with median and interquartile range (IQR). Normal distribution assumption will be evaluated using the Shapiro Wilk test. All analyzes will be done in Stata 16.0® (StataCorp, College Station, Texas, USA).

6.1. Primary outcome

The main analysis will be the survival analysis for the primary outcome variable (time to disappearance of symptoms associated with COVID-19), using the log-rank test to compare ivermectin versus placebo as a control group. Symptom resolution will be assessed using the 8-point ordinal scale, which has the following categories: (0) -Patient without symptoms, (1) -Non-hospitalized patient, with the ability to do daily activities, (2) -Non-hospitalized patient, unable to do daily activities, or using oxygen at home (3) -Hospitalized, without need for supplemental oxygen, (4) -Hospitalized, with need for supplemental oxygen, (5) -Hospitalized, with need for high-flow nasal oxygen or non-invasive mechanical ventilation, (6) -Hospitalized, in need of mechanical ventilation or ECMO, (7) -Death.

The outcome variable will be the time to recovery, defined as the first day, during the 21 days of follow-up, in which the patient reports a score of (0) on the 8-point scale.

Patients who do not report recovery from symptoms and those who die during study follow-up will be considered as censor data on day 21 or until death. Kaplan-Meier estimator will be used to report the recovery percentage throughout the follow-up and at day 21. Relevant treatment efficacy parameter is the recovery rate ratio (RR) with its respective 95% confidence interval (CI), which will be estimated by Cox proportional-hazard model. Given that the primary outcome may take two values; equal to 1 when the patient reports recovery of symptoms and 0 when not, a $RR > 1$ will indicate a favorable result for ivermectin compared to placebo.

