4.1.6. Other variables

In the data collection form, the baseline characteristics of the research participants will be measured, including sociodemographic variables, comorbidities and the “NEWS-2 score” that will be adjusted for secondary analyzes if they are associated with the outcomes.

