4.4 Sample size

According to the literature and previous data in this study, 75% of the subjects will have the event of interest (disappearance of symptoms) by day 21. Thus, including 390 subjects, we will identify 290 events of interest. With this sample size we will have a power of 80% and an Alpha of 0.05 to detect a Hazard ratio of 1.4 of ivermectin vs. placebo in time to symptom resolution. Taking into account a 2 % follow-up loss and 76 subjects who will be excluded from the primary analysis¹, we will include a total of 476 subjects in the study.

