The analysis of the primary outcome will be repeated using the population under the per protocol approach and will be considered as sensitivity analysis. Additionally, if differences are found between the research product and the outcomes, it will be evaluated whether variables such as enrollment score on the 8-point scale, duration of symptoms before enrollment, comorbidities, age and sex, modify the effect of the intervention groups, using a multivariate Cox proportional hazards model. This will be done by including interaction terms to the model between the possible modifying variable and the intervention groups. A p value <0.10 will be considered as a possible modifying effect, and a p value <0.05 will be considered as a cut-off point to confirm a significant interaction and therefore, to estimate the effect of the treatment groups with their respective 95% CI.

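### SAP 6.1 leaves already-collected baseline predictors out of the primary comparison; prespecified adjustment would gain efficiency, although the unadjusted test is valid and meets its stated power

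*Supplement*

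**What the plan says.** **Primary analysis.** SAP 6.1 (version of 20 September 2020) tests the primary outcome "using the log-rank test to compare ivermectin versus placebo as a control group". The effect measure is the recovery rate ratio, "which will be estimated by Cox proportional-hazard model". No covariate or stratum is named there or in protocol 4.5.

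**Design.** Protocol 4.2.4 randomises 1:1 in blocks of 4 with no stratification factor. Mild illness (protocol 4.1.5.3) covers outpatients and inpatients on supplemental oxygen below high flow, which is levels 1 to 4 of the ordinal scale. Onset may be up to 7 days earlier (4.2.1).

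**Baseline variables.** The ordinal score is taken at the randomisation visit and demographic data at screening (4.3.3). SAP 6.3 lists "enrollment score on the 8-point scale, duration of symptoms before enrollment, comorbidities, age and sex", but only as interaction terms, and only if a treatment difference is found.

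**Secondary analyses.** Protocol 4.1.6 says that baseline characteristics and NEWS-2 are variables "that will be adjusted for secondary analyzes if they are associated with the outcomes". Protocol 4.5 still plans a bivariate analysis of treatment, demographic and clinical variables against the secondary outcomes. The SAP's summary of changes removes the adjusted secondary analyses on the ground that randomisation balances the arms, and the current SAP 6.2 contains none.

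**The concern.** The outcome is the first day with a score of 0 within 21 days. A person who enters at level 1 on day 6 of illness and one who enters at level 4 on day 2 plausibly differ in time to reach it. Neither the allocation nor the analysis accounts for this.

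Expected balance between arms does not settle the matter. In a Cox model, leaving out a prognostic variable pulls the treatment ratio towards 1 relative to the ratio conditional on that variable, even when the arms are balanced. Adjustment can therefore make the test more sensitive at the same number of events, and it also removes the effect of chance imbalance in those variables. What is at stake is sensitivity that the trial could gain from data it already holds.

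For the secondary outcomes, choosing adjusters by their observed association lets the model depend on the results. The protocol and SAP also no longer agree on whether any adjusted secondary analysis is planned.

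**Working it through.** **1. The plan's own figure.** Inputs from protocol 4.4: a target "to detect a Hazard ratio of 1.4 of ivermectin vs. placebo in time to symptom resolution", "a power of 80% and an Alpha of 0.05", "75% of the subjects will have the event of interest (disappearance of symptoms) by day 21", and "including 390 subjects, we will identify 290 events of interest". Sidedness is not stated; two-sided is assumed.

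- Events, Freedman: (1.96 + 0.8416)² × [(1 + 1.4)/(1.4 − 1)]² = 7.849 × 36 = 282.6, so 283.
- Events, Schoenfeld: 4 × 7.849/(ln 1.4)² = 31.396/0.1132 = 277.3, so 278.
- Power at 290 events, Schoenfeld: Φ(√290 × 0.3365/2 − 1.96) = Φ(0.905) = 0.817.
- Power at 290 events, Freedman: Φ(√290 × 0.4/2.4 − 1.96) = Φ(0.878) = 0.810.
- Events expected: 390 × 0.75 = 292.5.

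The stated 290 events and 80% power reproduce for the unadjusted comparison.

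**2. What adjustment would add.** The documents give no prognostic strength, so I assumed a range. The simulation used 390 subjects 1:1, exponential times, 75% recovered by day 21, three independent normal covariates with combined log-hazard SD as shown, and 3000 runs per setting. The log-rank test was compared with the Wald test from a Cox model adjusted for all three. Monte Carlo error is about 0.7 point per power figure.

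The protocol does not say whether its 1.4 is an unadjusted or a conditional ratio, so both readings are shown (power, log-rank / adjusted):

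| Combined SD | Unadjusted ratio held near 1.4 | Conditional ratio held at 1.4 |
|---|---|---|
| 0 | 0.791 / 0.788 | 0.810 / 0.805 |
| 0.2 | 0.817 / 0.829 | 0.810 / 0.823 |
| 0.3 | 0.829 / 0.855 | 0.786 / 0.817 |
| 0.5 | 0.812 / 0.891 | 0.726 / 0.821 |
| 0.7 | 0.792 / 0.934 | 0.632 / 0.809 |

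Gains: at SD 0.3, 2.6 and 3.1 points; at 0.5, 7.9 and 9.5; at 0.7, 14.2 and 17.7. At SD 0, adjustment costs 0.3 to 0.5 point.

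**3. Where the gain comes from.** At SD 0.5 with the unadjusted ratio near 1.4, the mean unadjusted estimate is 1.392 (SE 0.1176) and the mean adjusted estimate 1.457 (SE 0.1187).

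- Unadjusted: ln 1.392/0.1176 = 0.3307/0.1176 = 2.81, power Φ(2.81 − 1.96) ≈ 0.80.
- Adjusted: ln 1.457/0.1187 = 0.3764/0.1187 = 3.17, power Φ(3.17 − 1.96) ≈ 0.89.

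The standard error rises slightly. The gain comes from a larger conditional ratio, not from better precision on the same ratio.

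**4. Robustness.** With the conditional ratio at 1.4, a separate run of 1500 per setting gave 0.78 / 0.82 at SD 0.3, 0.72 / 0.81 at 0.5 and 0.61 / 0.82 at 0.8, the last a gain of 21 points. With recovery recorded only at the scheduled contacts (days 2 to 5, 8, 11, 15, 21; Efron ties; 400 runs), the figures were 0.81 / 0.81 at SD 0, 0.80 / 0.83 at 0.3, 0.73 / 0.81 at 0.5 and 0.62 / 0.81 at 0.8. In that setting, type I error at SD 0.5 was 0.045 unadjusted and 0.058 adjusted (Monte Carlo SE about 0.011), so neither differs clearly from 0.05.

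**The case against.** The strongest objection is that nothing is broken. An unadjusted log-rank test is valid in a randomised trial, and this one is sized for exactly that test. A reader might infer that omitting predictors leaves the trial short of power, or biases the ratio below a true 1.4. The documents do not support that. Both statements require 1.4 to be a conditional ratio, and protocol 4.4 does not say so. If 1.4 is the unadjusted ratio that the planned test targets, log-rank power stays at 0.79 to 0.83 for every covariate strength in the table. This part of the objection stands in full.

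A reader might also infer that adjusters for the primary outcome will be picked by observed association. They will not: the rule in protocol 4.1.6 concerns secondary analyses only, and the latest SAP has dropped even those.

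The size of the gain is also uncertain. Entry is restricted to mild disease with onset within 7 days, and people contacted on days 5 to 7 after at least 48 hours of progressive improvement are excluded. Fewer than 3% had worsened by two points when Amendment 3 was written. A narrow range of prognosis could put the gain in the 0 to 3 point band, and levels 3 and 4 may be sparse. This stands as a limit on the size, not on the direction.

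Finally, adjustment is free only in data collection. It changes the estimand and needs a missing-covariate rule, and the only existing one (SAP 6.5) imputes the median of the patient's own arm. The choice of covariates is also open to debate: NEWS-2 and comorbidities are other candidates. These points shape the fix but do not defeat it.

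**Conclusion.** The point holds as an efficiency improvement. The primary analysis is valid and reaches 81 to 82% power at 290 events, but it makes no use of baseline information that the SAP itself treats as relevant to the outcome. Prespecified adjustment risks about half a point of power at most. It would add about 3 points at a combined log-hazard SD of 0.3, 8 to 10 at 0.5, and 14 to 21 at 0.7 to 0.8.

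These gains rest on an assumed prognostic strength, normal covariates, proportional hazards and a two-sided 0.05 test. The direction is secure; the size cannot be derived from the documents.

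For the secondary outcomes there is a smaller, separate point. Protocol 4.1.6 and 4.5 disagree with the current SAP, and neither the association-based rule nor the appeal to balance is a good basis for deciding on adjustment.

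**What to change.** - **SAP 6.1:** take the primary ratio and test from a Cox model with treatment plus a fixed list: ordinal score at randomisation (sparse levels pooled, for example 1, 2, 3 to 4), days from onset, and age (both continuous). State that the ratio is conditional on these covariates. Report the unadjusted log-rank test and ratio as supportive.
- **SAP 6.5:** impute any missing adjustment covariate without regard to arm; do not carry over the arm-specific median.
- **SAP 6.2:** add the randomisation score to each ordinal logistic model.
- **Protocol 4.1.6 and 4.5 (secondary analyses only):** replace selection by association with the same fixed list, and bring the protocol and SAP into agreement on whether adjusted secondary analyses are done.

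If other covariates such as NEWS-2 are preferred, the list should still be fixed before outcomes are seen by arm.

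The cost is SAP and protocol wording and a few lines of code; no new data are needed. The downside is that the primary estimand becomes a conditional ratio and a covariate missing-data rule has to be written.

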4.3.2. Study Procedures

The following procedures have been designed to meet the objectives of the study, reducing interaction between study personnel and research participants with COVID-19:

Once a subject with a positive antigen detection test or PCR for SARS-CoV-2 / COVID-19 has been identified, the principal or sub-investigator will contact the subject by telephone to provide study information through the telephone informed consent process. Subjects who express interest will be surveyed to obtain clinical and socio-demographic data and will be personally visited at their home or hospitalization site to sign the informed consent form in the presence of two witnesses.

At the screening visit, demographic data will be confirmed, informed consent will be signed, a blood sample will be obtained for liver enzyme evaluation, a pregnancy test (for women of childbearing age) and the participant's weight will be measured.

At the randomization visit, it will be determined whether or not the subject meets the selection criteria, including verification of liver enzyme result and pregnancy test (for women of childbearing age). Once it is defined that the subject meets the selection criteria. The research participant will be randomized, the necessary clinical data will be obtained, vital signs will be taken, and the investigation product will be initiated.

The administration of the research product will be done by self-administration in case of outpatient research participants, and in the case of hospitalized participants the administration instructions will be given to the subject and / or the health personnel who attends him/her, complying with the requirements of the institution.

Research participants will be contacted daily by phone call to remind them to take the research product, assess drug adherence, and detect adverse events to the research product.

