4.3.3 Table of visits and follow-ups

| Visit number (V) | Screening | Randomization | Phone call 1 | Phone call 1 | Phone call 1 | Phone call 1 | Phone call 1 | Phone call 1 | Phone call 1 | Phone call 1 |
|---|------------|---------------|-----------------|-----------------|-----------------|-----------------|-----------------|-----------------|-----------------|-----------------|
| Study deadlines | SCR | D1 | D2 | D3 | D4 | D5 | D8 | D11 | D 15 | D 21 |
| Intervals (days) | | | | | | | ±1 | ±1 | ±1 | ±1 |
| Signed informed consent form | X | | | | | | | | | |
| Inclusion/exclusion criteria | X | X | | | | | | | | |
| Assignment of the research participant number | X | | | | | | | | | |
| Demographic Data | X | | | | | | | | | |
| Medical background check | | X | | | | | | | | |
| Weight | X | | | | | | | | | |
| Vital signs and pulse oximetry | | X | | | | | | | | |
| Calculation of NEWS -2 score: | | X | | | | | | | | |
| Collection of clinical data | | X | | | | | | | | |
| Urine sample to evaluate pregnancy | X | | | | | | | | | |

| | | | | | | | | | | |
|---|-----------------------|----------|----------|----------|----------|----------|----------|----------|----------|----------|
| Blood Sample to evaluate Hepatic enzymes ² | X ² | | | | | | | | | |
| Randomization | | X | | | | | | | | |
| Dispensing and initiating medication/placebo | | X | | | | | | | | |
| Evaluation of the 7-point ordinal scale | | X | X | X | X | X | X | X | X | X |
| Assessment of secondary outcomes - Pt. at home or hospitalized? - Has required oxygen? - Has required ICU? - Vital status - Persists with fever? | | X | X | | | X | X | X | X | X |
| Collection of Serious Adverse Events (SAE) | | | X | | | X | X | X | X | X |
| Pharmacotherapeutic Adherence | | X | | | | X | | | | |
| Remember the need to take the investigation product | | | X | X | X | X | | | | |
| Collect symptoms reported to the admin of the investigation product | | | X | X | X | X | X | X | X | X |
| Record of completion | | | | | | | | | | X |

¹ In the case of hospitalized research participants, the study staff will personally visit the subject and/or contact the physician in charge by telephone, and/or through the medical history will obtain the necessary information and thus be able to determine primary or secondary outcomes

² It will not be necessary to collect the liver enzyme sample if there is a recent result no more than 3 days prior to selection.

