4.3.5 Follow up

To evaluate the evolution of the research participants and determine safety and efficacy according to the primary and secondary outcomes, subjects will be called on days 2, 3, 4, 5, 8, 11, 15 and 21 to fill out a questionnaire. In the event that the research participant requires hospitalization, the research participant will be visited personally to extract the information from the medical record. On the 21st day, the study will finish the evaluation of primary and secondary outcomes. In the case of hospitalized research participants, follow-up will continue until the end of hospitalization to determine their vital status.

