| 6.3. Sensitivity Analysis and Modification of the Effect for the Primary Outcome | 9 |
| 6.4. Safety Analysis | ¡Error! Marcador no definido. |
| 6.5. Handling Missing Data..... | ¡Error! Marcador no definido. |

1. Introduction

The purpose of this study is to assess whether D11AX22 molecule (ivermectin) reduces the time to resolution of symptoms (primary outcome variable), as well as the proportion of hospitalization, use of supplementary oxygen and number of cases with fever or more than two points on the eight-point ordinal scale for COVID (secondary outcome variables), compared to placebo in subjects with mild COVID-19 disease. This document describes definitions and statistical methods to be used in order to fulfill EPIC trial aim and objectives.

2. Study Design

Double-blind, randomized, placebo-controlled clinical trial to evaluate the efficacy of the D11AX22 (ivermectin) molecule in adult subjects with mild SARS CoV2/COVID-19 disease at participating institutions in Valle del Cauca.

This study is a controlled clinical trial with two parallel group with an allocation ratio of 1:1. Ten clinical visits will be made at the following times: screening visit, randomization visit, day 2, day 3, day 4, day 5, day 8, day 11, day 15 and day 21.

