4.1. Primary outcome

-Time until the resolution of the symptoms in the two study groups. Number of days from randomization visit to the first symptom-free day (score of 0 on the 8-point scale). Variable measured during the 21 days of follow-up.

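### Recovery is scored at only eight calls, yet the SAP names no method for tied times in the Cox model that gives the primary recovery ratio

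*Supplement*

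**What the plan says.** SAP 4.1 defines the primary outcome as "Number of days from randomization visit to the first symptom-free day" and adds in brackets that this means a score of 0 on the 8-point scale. SAP 6.1 puts it in terms of what is reported, so that recovery time is "defined as the first day, during the 21 days of follow-up, in which the patient reports a score of (0) on the 8-point scale".

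Protocol 4.3.5 fixes when patients can report: "subjects will be called on days 2, 3, 4, 5, 8, 11, 15 and 21 to fill out a questionnaire". SAP section 2 lists the same days. In the visit table (protocol 4.3.3) the ordinal scale, still called the 7-point scale there, is marked at randomization and on those eight days only. A window of one day either side applies to days 8, 11, 15 and 21.

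Protocol 4.3.2 also says "Research participants will be contacted daily by phone call to remind them to take the research product", but the stated purposes are reminders, adherence and adverse events. It adds no scale scores.

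For the analysis, SAP 6.1 tests the primary outcome "using the log-rank test to compare ivermectin versus placebo as a control group" and reports a recovery rate ratio with a 95% interval, "which will be estimated by Cox proportional-hazard model". The software is Stata 16. Neither SAP 6.1, SAP 6.3 nor protocol 4.5 names a method for tied times or a grouped-time or interval-censored model. None says which date is assigned when symptoms end between two calls.

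**The concern.** After day 5 the calls are 3, 3, 4 and 6 days apart. If the call day is the recorded day, a patient whose symptoms end on day 16 enters the analysis as recovered on day 21. Many recoveries then carry the same date: 290 events over eight dates average 36 per date.

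A Cox model is built for times with few ties. With ties this heavy, the estimated ratio depends on how the likelihood treats them, and the plan leaves that open. Two things are at stake. The headline ratio may not estimate the hazard ratio on which the trial was sized. Its interval may also disagree with the log-rank test, which is awkward when the test decides and the interval is quoted.

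**Working it through.** **Inputs.** From SAP 2.2: 390 evaluable subjects, 290 events, 75% recovered by day 21, ratio 1.4, alpha 0.05 (taken as two-sided), power 80%. Allocation is 1:1 (SAP section 2) and the call days are from protocol 4.3.5. Randomization is day 1, so day 21 is 20 days later. The shape of the recovery-time distribution is not given; Weibull shapes from 0.7 to 2 are assumed, and shape 1 is exponential.

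**The plan's own figure.**
- Freedman: (1.960 + 0.842)² × ((1.4 + 1)/(1.4 − 1))² = 7.849 × 36 = 283 events.
- Schoenfeld power at 290 events: Φ(√290 × ln 1.4 / 2 − 1.960) = Φ(0.905) = 81.7%.
- 0.75 × 390 = 292.5 events; 390/0.98 = 398; 398 + 76 = 474, against 476 in the plan.

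The event count and power reproduce.

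**How heavy the ties are.** With exponential times, the expected recoveries at the eight calls are about 27, 25, 23, 21, 56, 45, 47 and 49.

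**Why the tie method matters.** Let H be the placebo cumulative hazard over 20 days. From ½(e^−H + e^−1.4H) = 0.25, H = 1.178. For a gap of g days, h = 1.178 × g/20, and the chance of recovering within the gap is p₀ = 1 − e^−h on placebo and p₁ = 1 − e^−1.4h on ivermectin.

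| Gap (days) | p₀ | p₁ | p₁/p₀ | Odds ratio |
|---|---|---|---|---|
| 1 | 0.057 | 0.079 | 1.38 | 1.42 |
| 3 | 0.162 | 0.219 | 1.35 | 1.45 |
| 4 | 0.210 | 0.281 | 1.34 | 1.47 |
| 6 | 0.298 | 0.390 | 1.31 | 1.51 |

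Breslow solves Σ[d₁ − d·n₁θ/(n₁θ + n₀)] = 0 over call days, where d is the number recovering, n the number at risk, and subscripts 1 and 0 are ivermectin and placebo. It thus averages the p₁/p₀ column, and every entry is below 1.40. The exact-discrete likelihood averages the odds-ratio column, which is above 1.40. The complementary log-log model, p = 1 − exp(−exp(αⱼ + βx)), inverts the grouping and returns 1.40.

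**Large-sample estimates when the truth is 1.40.**

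| Method | Exponential | Shapes 0.7 to 2 |
|---|---|---|
| Breslow | 1.353 | 1.32 to 1.36 |
| Efron | 1.398 | 1.39 to 1.40 |
| Complementary log-log | 1.400 | 1.40 |
| Exact-discrete | 1.449 | 1.44 to 1.48 |

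On the log scale, Breslow in the exponential case loses 1 − ln 1.353/ln 1.40 = 1 − 0.302/0.336 = 10%.

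**Effect of the visit windows.** If later calls are spread evenly over the one-day windows, simulated Breslow estimates are about 1.35 to 1.37 and Efron 1.38 to 1.39.

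**Test and interval (simulated, 390 subjects).**
- Log-rank power on call-day data is 82.5%, against 83.0% on exact times (shape 1), and 81.6% against 82.3% (shape 1.5). With windows (shape 1) it is 80.2% against 81.2%.
- Log-rank type I error is 4 to 6%, with grouped or exact times.
- Breslow 95% interval coverage of 1.40 is about 96% (94 to 97% across settings).
- The Breslow interval includes 1 while log-rank rejects in 5.5, 5.8 and 8.9% of trials for shapes 0.8, 1.0 and 1.5 without windows, and in 3 to 4% with them.

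**The case against.** The strongest reply is that the designated primary test is the log-rank test, and it is nearly untouched. Both arms share one call schedule, so late dating is common to both, and grouping costs about one point of power or less. This stands. A reader might infer from the lower power of a Breslow Wald test (72 to 78% in the same simulations) that the trial is underpowered. The SAP does not designate that test, so the inference fails.

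The second reply is that the plan never says Breslow. This also stands. A reader might conclude that heavy ties must pull the ratio toward 1, but Efron shows almost no shift and exact-discrete moves the other way. The answer is that the plan does not choose. The same data could yield anything from about 1.32 to 1.48, and the choice could be made after the results are seen.

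Third, the call questionnaire is not shown, so callers may already ask when symptoms ended. With daily dates the Breslow estimate would be about 1.38, a much smaller shift. That is possible, but SAP 6.1 ties the event to the day a score is reported, and scores are scheduled only on call days.

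Finally, SAP 4.1 and 6.1 might be read as two conflicting endpoints. The documents do not support so strong a reading, because 4.1 also refers to a score of 0. What remains is an ambiguity about dates between calls.

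**Conclusion.** The point holds as a gap in the specification of the primary estimate. If Breslow is used, a true ratio of 1.40 would be reported at about 1.32 to 1.37, and in roughly 3 to 9% of trials under the design effect the interval would include 1 despite a significant log-rank test. Efron or a grouped-time proportional-hazards model gives about 1.38 to 1.41.

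The validity of the log-rank test, the trial's power and the coverage of the interval are not in question. Descriptively, recovery times are dated late by 1.4 to 1.9 days on average in the simulations without windows, and Kaplan-Meier medians would fall on days when calls were made.

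This rests on four assumptions: proportional hazards with Weibull recovery times, 75% recovered by day 21, the call day used as the recovery day, and Breslow as the method applied when none is named. The last is the least certain, and the direction of the shift depends on it.

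**What to change.** In SAP 6.1, name Cox regression with Efron ties as the source of the primary ratio and interval. A complementary log-log model with one intercept per call interval is an equally good choice. Exclude Breslow and the exact-discrete likelihood. A request for exact ties without further detail should be avoided, because it could admit the exact-discrete version.

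State in both SAP 4.1 and 6.1 that the recovery day is the call day on which a score of 0 is first reported. If the date on which symptoms ended is collected, use it in a sensitivity analysis only, since it depends on recall.

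The cost is a sentence or two of SAP text and one model option. No change to the sample size or the log-rank test is needed.
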